5.2.5 Previous and concomitant therapies

Therapies are collected in the **Previous/Concomitant Medication** eCRF, and terms are coded using the WHO drug code dictionary and the anatomic therapeutic chemical (ATC) class code using the versions available at database lock

A previous therapy is any treatment for which the end date is prior to the start of study (i.e., signing of informed consent). If the end date is missing and the start date of therapy is prior to the date of informed consent, then the therapy is considered as previous if ‘Ongoing at start of treatment?’ is not ticked with ‘Yes’.

A study-concomitant therapy is any treatment that is ongoing or initiated after signing of informed consent, or initiated up to 30 days after the DB study treatment discontinuation (Visit 8).

A double-blind treatment concomitant therapy is any treatment that is either ongoing at the start of DB study treatment (i.e., Day 1 – Visit 4 / Randomization) or is initiated during the DB treatment period.

Rules for handling partial or missing dates are detailed in Section 12.

Forbidden concomitant therapies

The following concomitant therapies are forbidden from Screening Visit (i.e., Visit 1) until the WD-EOT Visit (i.e., Visit 8):

- Any drug which may affect BP e.g., ophthalmic preparation, sympathomimetics (any formulation of decongestants), corticosteroids (intermittent use of topical/nasal applications excluded), cyclosporin, tacrolimus, erythropoietin, diet pills, herbal supplements, homeopathic compounds, treatment for psychiatric diseases [see protocol synopsis Appendix A].

- Endothelin receptor antagonists, and phosphodiesterase type-5 inhibitors.
- Strong inhibitors or inducers of cytochrome P450 3A4 isoenzyme [see protocol synopsis Appendix A].

These definitions will be used in the clinical review to identify potential PDs. Forbidden medication will not be tabulated as such.

Specific previous and concomitant therapies

Not applicable.

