Concomitant medication end date	If the answer to the question ‘Ongoing at start of treatment?’ in the Previous/Concomitant Medication eCRF is answered ‘No’ or if the study treatment start date-1 falls in the range of possible dates, the study treatment start date-1 is used. In all the other cases the upper limit is used.	No replacement. If the answer to the question ‘Ongoing at start of treatment?’ in the Previous/Concomitant Medication eCRF is answered ‘Yes’ the therapy is considered to have finished after the start of treatment.
Concomitant medication start date	
If the end date of the medication is not before the informed consent signature date and if the informed consent date falls in the range of possible dates, the informed consent date is used.
 
If the end date of the medication is not before the study treatment start date and if the study treatment start date falls in the range of possible dates, the study treatment start date is used.
 
In all the other cases the lower limit is used.
	No replacement. The medication is considered to have started before the date of consent.

Type of date	Date is incomplete	Date is missing
Hospitalization discharge date	The upper limit is used.	No replacement. The hospitalization is considered as ongoing in the analysis.
Hospitalization admission date	If the onset date of the AE leading to hospitalization falls in the range of possible dates, the onset date of the AE is used. In all the other cases the lower limit is used.	The onset date of the AE leading to hospitalization is used.

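### The SAP rule for incomplete concomitant-medication end dates joins its two conditions with 'or', so it can give end dates that contradict the eCRF answer, the recorded month or the drug's own start date

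*SAP*

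**What the plan says.** SAP Section 12 tabulates how incomplete and missing dates are replaced. For an incomplete concomitant-medication end date there are two triggers for using the day before study treatment start: the eCRF question on whether the drug was ongoing at treatment start is answered 'No', "or if the study treatment start date-1 falls in the range of possible dates, the study treatment start date-1 is used". Otherwise, "In all the other cases the upper limit is used". The neighbouring cell covers a wholly missing end date: nothing is imputed, and if the answer is 'Yes', "the therapy is considered to have finished after the start of treatment".

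In the next row, an incomplete start date depends on the end date. Treatment start is used only "If the end date of the medication is not before the study treatment start date" and treatment start is a possible date. A parallel rule for the consent date comes first, and the lower limit is used otherwise.

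SAP Section 5.2.5 sets the classes. A therapy is previous if it ended before consent. "A study-concomitant therapy is any treatment that is ongoing or initiated after signing of informed consent". A therapy is double-blind concomitant if it was ongoing at double-blind start "or is initiated during the DB treatment period". SAP Section 10.4.5 lists all therapies whatever their class.

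**The concern.** The two triggers should limit each other, but 'or' lets each act alone. The 'No' trigger is not confined to the recorded month, so it can overwrite a part of the date that the site did supply. The range trigger is not confined to 'No', so it can overrule a recorded 'Yes'. Neither is checked against the drug's start date.

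At stake is the accuracy of the previous, study-concomitant and double-blind concomitant therapy tables (SAP Section 13.3.5), which show what else subjects took around and during treatment. In a blood pressure trial these tables should not contain impossible dates or drop a drug that the site recorded as continuing into treatment.

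**Working it through.** The plan gives no figure to reproduce. The check applies the written rules to example records.

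**Rules.** Let T be study treatment start, read as double-blind start, and R the range of possible end dates.
- End = T − 1 if the answer is 'No' or T − 1 lies in R; otherwise the upper limit of R (SAP Section 12).
- An incomplete start becomes consent if the end is not before consent and consent is possible; T if the end is not before T and T is possible; otherwise the lower limit (SAP Section 12).
- Classes as in SAP Section 5.2.5.

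**Assumed dates.** In (a) and (c), consent is 2 February 2016 and T is 15 March 2016. In (b), consent is 5 June and T is 17 July. Both gaps are 42 days, the six-week run-in.

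**(a) 'Yes', start 1 January, end '-- March'.** R is 1 to 31 March and T − 1 = 14 March lies in it, so the end becomes 14 March. By its dates the drug was not ongoing at T and leaves the double-blind concomitant set, although the site answered 'Yes'. With the whole end date missing, the same drug counts as finished after start. The less complete record is classified better.

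**(b) 'No', end '-- May'.** Protocol Section 5.2.2 requires a previous therapy to be recorded only if it stopped less than 14 days before consent, here after 22 May. The true end therefore lies in 23 to 31 May, before consent. The 'No' trigger gives T − 1 = 16 July. That is 30 + 16 = 46 days after 31 May, outside the recorded month and after consent. The drug becomes study-concomitant; the upper limit, 31 May, would have left it previous.

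**(c) Drug first taken on treatment, 'No'.**
- Start 20 April, end '-- April': the end becomes 14 March, 17 + 20 = 37 days before the drug's own start. The start still falls in the double-blind period, so the drug stays double-blind concomitant and study-concomitant.
- Start '-- March', end '-- March': the end becomes 14 March. That is before T, so the start falls to the lower limit, 1 March. The record reads 1 to 14 March and leaves the double-blind table, but remains study-concomitant.

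**Enumeration of (c).** All double-blind start days in 2016, drug starts 1 to 55 days later and durations of 0 to 30 days give 366 × 55 × 31 = 624,030 records, all marked 'No', with consent 42 days before T.

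| Day missing from | End before start | Lost from double-blind table | Lost from study-concomitant table |
|---|---|---|---|
| End only | 100% | 0% | 0% |
| Start and end | 74.9% | 25.1% | 0% |

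The 25.1% are drugs that start in the same calendar month as T. These percentages describe the grid; they do not estimate the trial's records.

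**Would 'and' in place of 'or' be enough?** No. It repairs (a), which becomes 31 March, and the April record in (c), which becomes 30 April. A drug marked 'No' that starts on 20 March and ends '-- March' still becomes 14 March, before its own start.

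**The case against.** The strongest reply is that the practical effect is small, and most of it stands. The outputs concerned are descriptive, none of the therapy tables in SAP Section 13.3.5 is marked as key, and no efficacy analysis in SAP Table 4 uses medication end dates. Case (c) also assumes that sites answer 'No' for a drug started later. That is the natural answer, but neither document states it, and a blank may be possible.

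Two stronger readings are tempting, and the documents support neither. A reader might infer that drugs first taken on treatment drop out of the concomitant-therapy data. They generally do not: the second limb of the double-blind definition uses only the start date, study-concomitant therapy includes anything begun after consent, and every therapy is listed. Loss from the double-blind table in case (c) needs an incomplete start date as well.

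A reader might also infer that the Per-Protocol Set is affected, because SAP Section 5.2.5 says "These definitions will be used in the clinical review to identify potential PDs". That sentence follows the list of forbidden therapies and concerns which drugs are forbidden. SAP Section 6 identifies exclusions by protocol-deviation codes, and nothing there brings in imputed dates.

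Nor should case (b) be stretched to drugs stopped months before consent, since the 14-day limit means that the protocol does not ask for those records.

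What the reply does not remove is the rule itself. Case (a) needs no assumption about how sites answer, and contradicts both the recorded answer and the adjacent cell.

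**Conclusion.** The concern holds as a defect in one imputation rule. It produces contradictory dates in (a), dates outside the recorded month in (b) and impossible dates in (c). Misclassification follows in (a), in (b), and in (c) only when the start date is also incomplete. The size is limited to medication records with an incomplete end date; the documents do not give their number. The consequence lies in the descriptive previous and concomitant therapy tables. No effect on the Per-Protocol Set or the primary analysis is shown.

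The conclusion assumes that the rule is programmed as written and that study treatment start means double-blind start. The row does not say which start is meant, while SAP Sections 11.2 and 11.5 define run-in and double-blind starts separately. Case (b) in particular depends on the double-blind reading. Case (c) also assumes a 'No' answer.

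**What to change.** Replace the text for an incomplete end date with:

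> Impute the end date before the start date, and always within the range that the recorded parts allow. Use double-blind treatment start minus one day only if all three hold: the answer is 'No'; the recorded start date, or the whole range of possible start dates, is before double-blind treatment start; and that day is a possible end date. In all other cases (answer 'Yes' or blank, range wholly before treatment start, or medication started on, after or possibly after treatment start) use the upper limit. The imputed end date must not be before the medication's own start date.

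State in the row that treatment start means double-blind treatment start. The fixed order matters because the incomplete-start rule depends on the end date; without it, a record with both dates incomplete would be circular.

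Under this text, (a) becomes 31 March and stays double-blind concomitant; (b) becomes 31 May and stays previous; the April record in (c) becomes 30 April. The record with both days missing in March ends on 31 March and starts on 15 March, so it is kept in the double-blind table.

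The cost is one SAP row and a few lines of code. A few ambiguous records will be counted as concomitant although the drug may have stopped before treatment.

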13 LIST OF SUMMARY TABLES, LISTINGS AND FIGURES

The table, listing, and figure naming conventions have three components: **Display** (T, L, F), **Name** (free text, in general not more than eight characters, but if required to maintain uniqueness up to a maximum of ten characters), **Suffix** (for example, for analysis sets, or subgroups, not longer than four characters). Multiple suffixes can be added; components/suffixes are separated by ‘_’. Example: *T_TEAE_SAF, summary table (T) of treatment-emergent adverse events (TEAE) on the SAF.*

The mock layout column refers to the BST standard Outputs Version 3.0 as of March 31, 2016.

A number of outputs have been identified as key outputs based on which an initial assessment of the dose-response relationship can be made. These are indicated with a ‘Yes’ in the ‘Key’ columns of the tables below.

13.1 Subject disposition

Output name	Display *	Title (Description)	Analysis set(s)	Key	Mock layout
DISP	T	Disposition of subjects	SCR	Yes	LAYDISP001
DISP_SITE	T	Disposition of subjects by site	SCR		LAYDISP001
SCRFAIL	T	Reasons for screening failure	SCR		LAYDISP002
SCRFAIL	L	Listing of reasons for screening failure	SCR		LSTCSR011
RUNFAIL	T	Reasons for run-in failure	RIS		LAYDISP002
RUNFAIL	L	Listing of run-in failures	RIS		LSTCSR011
ANSETOV	T	Overview of FAS, PPS, SAF and PK analysis sets	RND	Yes	LAYDISP001

Output name	Display *	Title (Description)	Analysis set(s)	Key	Mock layout
ANSET	L	Listing of subject participation in the different analysis sets	RND		LSTCSR031
RAND	L	Randomization scheme and codes	RND		LSTRAN
UNBLIND	L	Listing of code break or subject unblinding	RND		LSTCSR032

* T = Summary Table; L = Listing.

FAS = Full Analysis Set; PK = Pharmacokinetic; PPS = Per-Protocol Set; RIS = Run-in Set; RND = All Randomized Set; SAF = Safety Set; SCR = Screened Set.

13.2 Protocol deviations

Output name	Display *	Title (Description)	Analysis set(s)**	Key	Mock layout
PRDEVA	T	Important protocol deviations during the double-blind period	FAS		LAYPD001
PRDEVI	T	Protocol deviations leading to exclusion from PPS	FAS	Yes	LAYPD002
PRDEVA	T	Important protocol deviations during run-in period	RIS		LAYPD001
PRDEV	L	Listing of protocol deviations	SCR		LSTCSR021

* T = Summary Table; L = Listing.

FAS = Full Analysis Set; PPS = Per-Protocol Set; RIS = Run-in Set; SCR = Screened Set.

13.3 Subject characteristics

13.3.1 Demographics

Output name	Display *	Title (Description)	Analysis set(s)	Key	Mock layout
DEMOG	T	Demographic characteristics	FAS, PPS, PK	Yes	LAYDEM001
DEMOG	L	Listing of demographic characteristics	RIS		LSTCSR041
AGECATEU	T	EudraCT age categories	FAS		LAYDEM004

* T = Summary Table; L = Listing.

FAS = Full Analysis Set; PK = Pharmacokinetic; PPS = Per-Protocol Set; RIS = Run-in Set.

13.3.2 Baseline disease characteristics

Output name	Display *	Title (Description)	Analysis set(s)	Key	Mock layout
BASDC	T	Essential hypertension at Screening	FAS, PPS		LAYMIX001
BASDC	L	Listing of essential hypertension at Screening	SCR		LSTCSR091

* T = Summary Table; L = Listing.

FAS = Full Analysis Set; PPS = Per-Protocol Set; SCR = Screened Set.

13.3.3 Other baseline characteristics

Output name	Display *	Title (Description)	Analysis set(s)	Key	Mock layout
OBASDC	T	Height at Screening, weight and BMI at baseline	FAS, PPS, PK		LAYDEM001

* T = Summary Table; L = Listing.

BMI = body mass index; FAS = Full Analysis Set; PK = Pharmacokinetic; PPS = Per-Protocol Set;

13.3.4 Medical history

Output name	Display*	Title (Description)	Analysis set(s)	Key	Mock layout
MHSCPR	T	Medical history by primary system organ class (SOC) and preferred term	FAS		LAYMH001
CDSCPR	T	Concomitant disease by primary system organ class (SOC) and preferred term	FAS		LAYMH001
PCM HIST	L	Listing of subjects with previous and concomitant medical history	SCR		LSTCSR043

* T = Summary Table; L = Listing.

FAS = Full Analysis Set; SCR = Screened Set; SOC = system organ class.

13.3.5 Previous and concomitant therapies

Output name	Display*	Title (Description)	Analysis set(s)	Key	Mock layout
PTATCPR	T	Previous therapies by anatomical therapeutic chemical (ATC) class and preferred term	FAS		LAYCONMED001
DBCATCPR	T	Double-blind treatment concomitant therapies by anatomical therapeutic chemical (ATC) class and preferred term	FAS		LAYCONMED001

Output name	Display*	Title (Description)	Analysis set(s)	Key	Mock layout
STCATCPR	T	Study-concomitant therapies by anatomical therapeutic chemical (ATC) class and preferred term	FAS		LAYCONMED001
PCTHER	L	Listing of subjects with previous and concomitant therapies	RIS		LSTCSR044

* T = Summary Table; L = Listing.

ATC = anatomical therapeutic chemical; FAS = Full Analysis Set; RIS = Run-in Set.

13.3.6 Specific previous and concomitant therapies

Not applicable.

13.3.7 Other subject characteristics

Not applicable.

13.4 Study treatment duration and compliance

13.4.1 Study treatment duration

Output name	Display*	Title (Description)	Analysis set(s)	Key	Mock layout
TREXP	T	Double-blind treatment duration	FAS, PPS, SAF	Yes	LAYEX001
TREXP	T	Run-in treatment duration	RIS		LAYEX001
TREXP	L	Listing of run-in and double-blind treatment duration	RIS		LSTCSR052

* T = Summary Table; L = Listing.

FAS = Full Analysis Set; PPS = Per-Protocol Set; RIS = Run-in Set; SAF = Safety Set.

13.4.2 Compliance with study treatment

Output name	Display*	Title (Description)	Analysis set(s)	Key	Mock layout
COMPA	T	Compliance with double-blind study treatment	PPS, FAS		LAYCAT001
COMPA	T	Compliance with run-in study treatment	RIS		LAYCAT001
COMPA	L	Listing of compliance with double-blind study treatment	SAF		LSTCSR051a

* T = Summary Table; L = Listing.

FAS = Full Analysis Set; PPS = Per-Protocol Set; RIS = Run-in Set; SAF = Safety Set.

13.4.3 Study treatment discontinuation

Output name	Display*	Title (Description)	Analysis set(s)	Key	Mock layout
PDISCTR	T	Reasons for premature discontinuation of double-blind study treatment	SAF	Yes	LAYDISP003b
PDISCTR	T	Reasons for premature discontinuation of run-in treatment	RIS		LAYDISP003b
PDISCTR	L	Listing of subjects who discontinued treatment	RIS		LSTCSR012

* T = Summary Table; L = Listing.

RIS = Run-in Set; SAF = Safety Set.

13.4.4 Study treatment adjustments or interruptions

Output name	Display*	Title (Description)	Analysis set(s)	Key	Mock layout
TREINT	T	Reasons for double-blind treatment interruptions	SAF		LAYMIX001
TREINT	L	Listing of subjects with double-blind treatment interruptions	SAF		L_TREINT

* T = Summary Table; L = Listing.
SAF = Safety Set.

13.5 Study withdrawal

Output name	Display*	Title (Description)	Analysis set(s)	Key	Mock layout
PDISCST	T	Reasons for premature study discontinuation after randomization	RND		LAYDISP004b
PDISCST	T	Reasons for premature study discontinuation before randomization	RIS		LAYDISP004b
PDISC	L	Listing of subjects who discontinued the study prematurely	RIS		LSTCSR012

* T = Summary Table; L = Listing.
RIS = Run-in Set; RND = All Randomized Set.

13.6 Primary efficacy analyses

13.6.1 Main analysis

All outputs for the main analysis will be based on the PPS. Some outputs will also be generated for the FAS. These are listed in [13.6.2](#).

Output name	Display*	Title (Description)	Analysis set(s)	Key	Mock layout
DBP_VIS	T	Mean trough sitting diastolic blood pressure (SiDBP) as measured by OBPM by visit and treatment group	PPS		LAYCON001
DBP_CHG	T	Change from baseline to post-baseline visits in mean trough sitting diastolic blood pressure (SiDBP) as measured by OBPM by treatment group	PPS	Yes	LAYBASE001
DBP_MCHG	F	Mean change from baseline to post-baseline visits in mean trough sitting diastolic blood pressure (SiDBP) as measured by OBPM by treatment group	PPS	Yes	LAYTIME
DBP_CHG	F	Density of change from baseline to post-baseline visits in mean trough sitting diastolic blood pressure (SiDBP) as measured by OBPM by treatment group	PPS		LAYDENS
DBP_MCPMOD1	T	MCP-Mod test for dose-response in change from baseline to Week 8 in mean trough sitting diastolic blood pressure (SiDBP)	PPS	Yes	LAYMCP1

Output name	Display*	Title (Description)	Analysis set(s)	Key	Mock layout
DBP_MCPMOD2	T	MCP-Mod estimation of dose-response in change from baseline to Week 8 in mean trough sitting diastolic blood pressure (SiDBP)	PPS	Yes	LAYMCP2
DBP_MCPMOD	F	MCP-Mod estimation of dose-response in change from baseline to Week 8 in mean trough sitting diastolic blood pressure (SiDBP)	PPS		LAYMCP3
DBP_MCPMOD_SEL	F	MCP-Mod estimation of dose-response in change from baseline to Week 8 in mean trough sitting diastolic blood pressure (SiDBP) - Best fitting model	PPS	Yes	LAYMCP4
DBP_MCPMOD_SEL	T	MCP-Mod estimation of dose-response in change from baseline to Week 8 in mean trough sitting diastolic blood pressure (SiDBP) - Best fitting model	PPS		LAYMCP5

* T = Summary Table; F = Figure.

PPS = Per-Protocol Set; MCP-Mod = Multiple Comparison Procedure – Modeling; OBPM = automated office blood pressure measurement; SiDBP = sitting diastolic blood pressure.

13.6.2 Supportive/sensitivity analyses

Output name	Display *	Title (Description)	Analysis set(s)	Key	Mock layout
DBP_VIS	T	Mean trough sitting diastolic blood pressure (SiDBP) as measured by OBPM by visit and treatment group	FAS		LAYCONO01
DBP_CHG	T	Change from baseline to post-baseline visits in mean trough sitting diastolic blood pressure (SiDBP) as measured by OBPM by treatment group	FAS	Yes	LAYBASE001
DBP_MCHG	F	Mean change from baseline to post-baseline visits in mean trough sitting diastolic blood pressure (SiDBP) as measured by OBPM by treatment group	PPS	Yes	LAYTIME
DBP_CHG	F	Density of change from baseline to post-baseline visits in mean trough sitting diastolic blood pressure (SiDBP) as measured by OBPM by treatment group	FAS		LAYDENS
DBP_MCPMOD1	T	MCP-Mod test for dose-response in change from baseline to Week 8 in mean trough sitting diastolic blood pressure (SiDBP)	FAS	Yes	LAYMCP1

Output name	Display *	Title (Description)	Analysis set(s)	Key	Mock layout
DBP_MCPMOD 2	T	MCP-Mod estimation of dose-response in change from baseline to Week 8 in mean trough sitting diastolic blood pressure (SiDBP)	FAS	Yes	LAYMCP2
DBP_MCPMOD	F	MCP-Mod estimation of dose-response in change from baseline to Week 8 in mean trough sitting diastolic blood pressure (SiDBP)	FAS		LAYMCP3
DBP_MCPMOD _SEL	F	MCP-Mod estimation of dose-response in change from baseline to Week 8 in mean trough sitting diastolic blood pressure (SiDBP) - Best fitting model	FAS	Yes	LAYMCP4
DBP_MCPMOD _SEL	T	MCP-Mod estimation of dose-response in change from baseline to Week 8 in mean trough sitting diastolic blood pressure (SiDBP) - Best fitting model	FAS		LAYMCP5
DBP_ANCOVA	T	ANCOVA for change from baseline to Week 8 in mean trough sitting diastolic blood pressure (SiDBP) - ACT-132577 vs placebo	PPS, FAS	Yes	LAYBETW 001

Output name	Display *	Title (Description)	Analysis set(s)	Key	Mock layout
DBP_ANCOVA	F	ANCOVA for change from baseline to Week 8 in mean trough sitting diastolic blood pressure (SiDBP) - ACT-132577 vs placebo	PPS, FAS	Yes	LAYFOR
DBP_ANCOVA_L	T	ANCOVA for change from baseline to Week 8 in mean trough sitting diastolic blood pressure (SiDBP) - Lisinopril vs placebo	PPS, FAS	Yes	LAYBETW001
DBP_MCPMBO_CF1	T	MCP-Mod test for dose-response in change from baseline to Week 8 in mean trough sitting diastolic blood pressure (SiDBP, BOCF)	FAS		LAYMCP1
DBP_MCPMBO_CF2	T	MCP-Mod estimation of dose-response in change from baseline to Week 8 in mean trough sitting diastolic blood pressure (SiDBP, BOCF)	FAS		LAYMCP2
DBP_MCPMBO_CF	F	MCP-Mod estimation of dose-response in change from baseline to Week 8 in mean trough sitting diastolic blood pressure (SiDBP, BOCF)	FAS		LAYMCP3

Output name	Display *	Title (Description)	Analysis set(s)	Key	Mock layout
DBP_MIXED_W2_W4_W8	T	Mixed Model for changes from baseline to Weeks 2, 4 and 8 in mean trough sitting diastolic blood pressure (SiDBP, OC) - ACT-132577 vs placebo	FAS		LAYBETW001
DBP_MIXED_W2_W4_W8_MCP1		Mixed Model for changes from baseline to Weeks 2, 4 and 8 in mean trough sitting diastolic blood pressure (SiDBP, OC) - MCP-Mod test for dose-response at Week 8	FAS		LAYMCP1
DBP_MIXED_W2_W4_W8_MCP2		Mixed Model for changes from baseline to Weeks 2, 4 and 8 in mean trough sitting diastolic blood pressure (SiDBP, OC) - MCP-Mod estimation of dose-response at Week 8	FAS		LAYMCP2
DBP_MIXED_W2_W4_W8_L	T	Mixed Model for changes from baseline to Weeks 2, 4 and 8 in mean trough sitting diastolic blood pressure (SiDBP, OC) - Lisinopril vs placebo	FAS		LAYBETW001
DBP_MIXED_AVER8	T	Mixed Model for average change from baseline to Weeks 2, 4 and 8 in mean trough sitting diastolic blood pressure (SiDBP, OC) - ACT-132577 vs placebo	PPS, FAS		LAYBETW001

Output name	Display *	Title (Description)	Analysis set(s)	Key	Mock layout
DBP_MIXED_AVER8_MCP1	T	Mixed Model for average change from baseline to Weeks 2, 4 and 8 in mean trough sitting diastolic blood pressure (SiDBP, OC) - MCP-Mod test for dose-response	PPS, FAS		LAYMCP1
DBP_MIXED_AVER8_MCP2	T	Mixed Model for average change from baseline to Weeks 2, 4 and 8 in mean trough sitting diastolic blood pressure (SiDBP, OC) - MCP-Mod estimation of dose-response	PPS, FAS		LAYMCP2
DBP_MIXED_AVER8_L	T	Mixed Model for average change from baseline to Weeks 2, 4 and 8 in mean trough sitting diastolic blood pressure (SiDBP, OC) - Lisinopril vs placebo	PPS, FAS		LAYBETW001

* T = Summary Table; L = Listing; F = Figure.

ANCOVA = analysis of covariance; BOCF = baseline observation carried forward; FAS = Full Analysis Set; MCP-Mod = Multiple Comparison Procedure – Modeling; OBPM = automated office blood pressure measurement; PPS = Per-Protocol Set; SiDBP = sitting diastolic blood pressure.

